10.3.2.2 Analysis for secondary variables

For the analysis of these variables, the same primary analysis will be performed as long as the necessary measurements are available.

10.3.3 Exploratory analysis

The analysis of exploratory variables, FR and body temperature, will be performed on those subjects who complete their participation without deviations from the study protocol (per-protocol population, PP).

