5.2 Criteria for elimination and/or substitution of subjects

5.2.1 Elimination criteria

- Withdrawal of informed consent.
- Major deviation from the protocol that could impact the integrity of the results.
- Presentation of an adverse event, whether or not related to the investigational product, which, in the opinion of the PI and/or the sponsor, could affect the subject's ability to safely continue the study procedures.
- Non-tolerability or hypersensitivity to any of the compounds used during the tests.
- Non-tolerability or hypersensitivity to the investigational product.

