7.4.5.10 Respiratory rate

This is the measurement of the number of breaths per minute taken by research subjects. It is assessed discreetly by observing, without the subject's awareness, the movements of the rib cage, counting each rise/rise of the subject's rib cage as one breath. A range of 12 to 24 breaths per minute is considered normal.

Management as an AE: Any abnormal value will be considered an adverse event. In some cases, the research subject may need to be considered a possible case of COVID-19, and the investigator may need to refer the patient for medical care and withdraw the subject from the research.

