7.4.5.11 Body temperature

It is the temperature level of a body. Normal values range from 35°C to 37.4°C. It can be measured using a contact or non-contact thermometer on different parts of the body. Any thermometer calibrated at the research center may be used in the study, as long as the same one is used for all patients and for all their visits.

Management as an AE: Any abnormal value will be considered an adverse event. In some cases, the research subject may need to be considered a possible case of COVID-19, and the investigator may need to refer the patient for medical care and withdraw the subject from the research.

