10.3.2 Safety and tolerability analysis

10.3.2.1 Analysis for primary variables

The analysis of safety and tolerability outcomes will be conducted in the safety population, defined as all subjects who received at least one dose of the investigational product (PRO-185), regardless of their adherence to the protocol (intention-to-treat, ITT, population).

Statistical analysis for the primary quantitative variables will be estimated using the Wilcoxon signed-rank test for a sample for the difference in measurements before and after treatment for visits 1 and 2, while the baseline visit (pre-PT) will be compared against the final visit, once the values have been adjusted with respect to their baseline within each individual.

For conjunctival hyperemia, the X^2 binomial test or Fisher's exact test will be used for expected values less than 5.

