10.4 Procedure for handling missing data

An imputation procedure for missing data is not contemplated.

11. Ethical considerations

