#### 6.3 Exploratory analysis

The analysis of exploratory variables, FR and body temperature, will be performed on those subjects who complete their participation without deviations from the study protocol (per-protocol population, PP).

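### Respiratory rate and body temperature are analysed only in deviation-free completers, although an abnormal value of either may lead to withdrawal, so abnormal values can be selectively excluded from that analysis

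*Protocol*

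**What the plan says.** - **Analysis set for the two variables.** Protocol 10.3.3 states that their analysis "will be performed on those subjects who complete their participation without deviations from the study protocol (per-protocol population, PP"). SAP 6.3 has the same rule: "The analysis of exploratory variables, FR and body temperature, will be performed on those subjects" who complete without deviations. Neither document plans an analysis of these variables in all dosed subjects.
- **What an abnormal value triggers.** Protocol 7.4.5.11 on temperature says "Any abnormal value will be considered an adverse event", and 7.4.5.10 treats respiratory rate the same way. Both add that in some cases, when COVID-19 is suspected, "the investigator may need to refer the patient for medical care and withdraw the subject from the research". Section 5.2.1 separately lists as a ground for elimination "Presentation of an adverse event, whether or not related to the investigational product", if in the opinion of the investigator or sponsor it could affect safe continuation.
- **Analysis set for other outcomes.** Protocol 10.3.2.1 uses the safety population for safety and tolerability outcomes. This set is "defined as all subjects who received at least one dose of the investigational product (PRO-185), regardless of their adherence to the protocol". Section 10.3.2.2 gives the secondary variables the same analysis where measurements exist. SAP 6.2.1 and 6.2.2 agree.
- **Missing data.** Protocol 10.4: "An imputation procedure for missing data is not contemplated". SAP 6.4.2 says the same.

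**The concern.** The trial's main objective is safety and tolerability, and both variables are vital signs. Temperature also has a pharmacological link: protocol 2.2.1 names a fall in body temperature among the effects of naphazoline overdose. A subject withdrawn because of an abnormal reading does not complete, so is outside the per-protocol set. The rule that selects the subjects is therefore tied to the outcome being analysed. No reason is given for treating these two variables differently from the primary and secondary ones. At stake is a summary of respiratory rate and temperature that looks cleaner than the adverse event listing from the same trial.

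**Working it through.** The plan states no figure on this point, so there is none to reproduce. The check has three parts.

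**1. Which values can be lost.** The activity schedule measures both variables at baseline, before treatment at visits 1 and 2, and at the final visit. Normal vital signs are required for inclusion, so an abnormal baseline value bars entry. A subject whose first abnormal value is at the final visit has already completed. The values exposed to this selection are therefore mainly those at visits 1 and 2 that lead to withdrawal.

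**2. Size, under assumed rates.** Let q be the true proportion of subjects with an abnormal value and r the probability of withdrawal given one. The documents give neither. Assume that other exclusions are unrelated to abnormality. The expected proportion among completers is then

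q(1 − r) / (1 − qr).

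| q | r = 25% | r = 50% | r = 100% |
|---|---|---|---|
| 5% | 0.0375/0.9875 = 3.8% | 0.025/0.975 = 2.6% | 0% |
| 10% | 0.075/0.975 = 7.7% | 0.05/0.95 = 5.3% | 0% |
| 20% | 0.15/0.95 = 15.8% | 0.10/0.90 = 11.1% | 0% |

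In counts, with the planned 22 subjects and no other exclusions:
- 2 abnormal, 1 withdrawn: 2/22 = 9.1% of all dosed, 1/21 = 4.8% of completers.
- 2 abnormal, both withdrawn: 9.1% against 0/20 = 0%.
- 3 abnormal, 2 withdrawn: 3/22 = 13.6% against 1/20 = 5.0%.

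This mechanism can only lower the observed proportion. It has no effect if no abnormal value leads to withdrawal.

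**3. The listed test.** Protocol Table iii lists the one-sample Wilcoxon signed-rank test for both variables, not a comparison of proportions. (SAP Table 2 lists Kolmogorov-Smirnov or Mann-Whitney.) Excluding subjects with large changes removes high-ranking differences. If these run in the direction of the overall shift, the evidence of change weakens; if they run against it, the evidence strengthens. Abnormal values can lie on either side of the normal range, so the direction of the effect on this test is not fixed.

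**A related inconsistency.** What counts as abnormal is not settled. For respiratory rate, Table iii gives 12–16 per minute and 7.4.5.10 gives 12–24. For temperature, Table iii gives 36.7–37.4 °C and 7.4.5.11 gives 35–37.4 °C. These ranges decide which values are adverse events, and so who may be withdrawn.

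**The case against.** The strongest reply is that the safety information is kept. Each abnormal value is an adverse event. Adverse event incidence is a secondary outcome (protocol 7.4.2) with the same analysis as the primary variables, hence in all dosed subjects, and section 5.5 continues follow-up of subjects withdrawn for adverse events. This stands. A reader might infer from the per-protocol rule that abnormal readings vanish from the trial; they do not. They can be missing only from the analysis of the variable itself.

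Other strong readings also go too far:
- **That every abnormal value is lost.** Withdrawal is discretionary and described for some cases only. A fall from 9.1% to 0% requires every affected subject to be withdrawn.
- **That the test is biased toward no change.** This holds for the proportion abnormal, but not necessarily for a signed-rank test.
- **That the analysis set alone prevents comparison with heart rate and blood pressure.** Respiratory rate and temperature have no post-treatment reading at visits 1 and 2, so the before-and-after comparison is unavailable in any population. With no imputation, a subject without a final-visit value also drops out of the baseline-to-final comparison for heart rate and blood pressure.
- **That low adherence removes subjects who stopped because of symptoms.** Section 6.4 says only that subjects below 80% adherence go into the intention-to-treat population. Their exclusion from the per-protocol set is an inference, and the documents say nothing of why they might stop.

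What remains is that the analysis set is partly selected on the outcome, without a stated reason.

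**Conclusion.** The point holds as a minor improvement. The population rule and the withdrawal provision are explicit, and together they allow selective exclusion of abnormal respiratory rate and temperature values from their own analysis. The size is unknown. The tabulated figures rest on assumed values of q and r and on other exclusions being unrelated to abnormality; they describe the proportion abnormal, not the Wilcoxon result. Both variables are exploratory and neither is in the hypothesis, so the conclusion on the primary outcomes does not change.

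**What to change.** Replace the sentence in protocol 10.3.3 and in SAP 6.3 with one along these lines: respiratory rate and body temperature will be analysed in the safety population using all available measurements, as change from baseline at visits 1, 2 and final, with the last on-study value used for subjects withdrawn early; the per-protocol result will be a sensitivity analysis.

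The last-value rule has to be written down. Changing the population alone would not bring an early-withdrawn subject back into the paired baseline-to-final test. Section 5.5 treats the withdrawal visit as the final visit for withdrawn consent or a major deviation, but does not say so for adverse events. The wording should define this value as the endpoint, so that it does not clash with the statement on imputation.

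Reconcile the normal ranges in Table iii (and SAP Table 2) with those in 7.4.5.10 and 7.4.5.11.

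No new measurement is needed and there is no statistical cost. The protocol sentence goes through the amendment process in section 11.2, so it is sensibly bundled with other changes.

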10.4 Procedure for handling missing data

An imputation procedure for missing data is not contemplated.

11. Ethical considerations

11.1 Approval of committees

This study will be conducted in accordance with the standards of the Declaration of Helsinki, World Medical Association 2013. Nuremberg Code ; Nuremberg Judgment by the International Tribunal at Nuremberg , 1947. Belmont Report, National Commission for the Protection of Subjects of Biomedical and Conduct Research, 1979. It will be conducted in accordance with the scientific and technical requirements necessary for the registration of medicines for human use of the International Conference on Harmonization (*The International Council for Harmonisation* (ICH) Guideline for Good Clinical Practice. International Ethical Guidelines for Biomedical Research Involving Human Subjects of the Council for International *Organizations of Medical Sciences of Medical Sciences* , CIOMS, 2002). International Ethical Guidelines for Epidemiological Studies of the Council for International *Organizations of Medical Sciences of Medical Sciences* , CIOMS, 2008). The Research Ethics Committee and the Research Committee will evaluate the protocol before conducting the study and will issue their approval or any possible modifications for its implementation. These Committees must be notified of any significant changes to the protocol. In addition to the above, the current regulations of the regulatory authority must also be complied with.

The sponsor's authorized personnel will submit the essential documentation of the research project for evaluation by the Research Ethics Committees, Research Committees, and when applicable, to the Biosafety Committee: research protocol, informed consent form, researcher's manual, subject material, as well as other additionally requested documents, in accordance with the local, national or international requirements applicable by regulatory entities.

The study will not be initiated at the research center without the confidentiality agreements and financial proposals from each of the principal investigators, duly signed, and without having previously obtained the favorable opinion and/or approval of the corresponding Research Ethics Committees, Research Committees, and, where applicable, the Biosafety Committee.

The study will not begin without meeting the relevant local, national, or international regulatory requirements and obtaining the appropriate health authorization.

The study is considered to be research with greater than minimum risk, in accordance with the Regulations of the General Health Law on Health Research, Title Two, Chapter I, Article 17, Section III, published in the Official Gazette on January 6, 1987.

11.2 Amendments to the protocol

The amendment process will be relevant when there is a need to make any changes to a document that is part of the research project or protocol, due to changes in the methodological structure, replacement of the principal investigator, or the identification of risks to the research subjects.

Documents that may be amended include: the protocol, informed consent letter, researcher's manual, subject documents, measurement scales, and activity schedule.

Any amendment must be approved by the sponsor and/or the principal investigator. The amended document(s), once reviewed and approved by the Research Ethics Committee and the Research Committee or, when applicable, by the Biosafety Committee (entities that issued the initial favorable opinion for the conduct of the research), will be sent for authorization by the regulatory entity.

Amendments that substantially modify the protocol or impose additional or different risks to research subjects must be approved by the aforementioned Committees. It is the investigator's responsibility to take measures in situations requiring immediate action to prevent unnecessary harm to study participants.

The principal investigator is responsible for communicating to the Research Ethics Committee any amendments to the protocol that could affect the rights, safety, or well-being of the research participants. They must also report any situation or new knowledge that indicates an increased risk to the participants, the premature termination or suspension of the study, the reasons for this, and the results obtained to that point. They must also report the conclusion of the study upon completion of the research protocol.

11.3 Early termination of the study

The study may be temporarily suspended or terminated prematurely if there is sufficiently reasonable cause. Written notification documenting the reason for the suspension or early termination must be provided by the party executing the suspension. The PI must promptly inform the study participants, the IC, and the IRB, providing the reasons.

Situations in which suspension or early termination of the study will be considered include, but are not limited to:

1. The presence of serious adverse events in more than 10% of participants in a study group.
2. The regulatory authority considers it to be a security alert.
3. The Sponsor determines it for its convenience or eventualities such as: financial support, manufacturing errors, etc.
4. The determination of unexpected risks to participants that are significant or unacceptable.
5. Obtaining new relevant safety information.
6. Insufficient adherence to protocol requirements.
7. The data obtained are not evaluable or are not sufficiently complete.
8. The determination that the primary objective has been achieved.
9. The determination of futility.

In the event of suspension, the study may be resumed once the situations that led to the suspension have been resolved, provided this justification is sufficient for the sponsor, IC, IEC, and regulatory authorities.

11.4 Informed consent

The FCI contains complete and understandable information about the study and the investigational product, in accordance with current applicable regulations and Good Clinical Practices.

The FCI will be considered a source document and will be filed as such. The site's principal investigator is responsible for ensuring that all new versions of the informed consent form undergo the appropriate approvals (the same ones that the original informed consent form underwent) and that the most current approved version is presented to the study subjects.

11.4.1 Obtaining

Informed consent must be obtained before the subject undergoes any procedure indicated in the protocol. For this purpose, the informed consent form must be signed.

Written consent documents will incorporate the elements of informed consent described in the Declaration of Helsinki and the ICH Guidelines for Good Clinical Practice and will be in compliance with all applicable laws and regulations.

The PI, or the study staff delegated by him or her, will provide the potential participant with all information regarding the characteristics of the study, its potential benefits, risks, objectives, and procedures.

This information will be provided in a language understandable to the subject. The subject will be explained that they have the right to discontinue their participation in the study at any stage, without affecting their relationship with the researcher and/or their future participation. Informed consent will be presented to the potential participant; they must have sufficient time to review each and every aspect mentioned above. Any questions they may have will be clarified by the person responsible for obtaining informed consent.

Once the participant agrees to participate in the study, he or she must sign and date the informed consent letter in the presence of two witnesses, whether or not related to the study subject. These witnesses will participate in the informed consent process and sign, confirming that the process was carried out prior to any study procedure, that the study information was clearly explained, and that any questions were clarified.

In the event that a subject is illiterate, acceptance will be with his or her fingerprint, and in the event that the subject is not capable of providing adequate written informed consent, a "legally authorized" representative of the subject may provide such consent for the subject in accordance with applicable laws and regulations.

Likewise, the PI, or the study staff delegated by him, must sign and date this consent.

The FCI must be signed in duplicate by all involved; one copy will be filed in the researcher's folder and the other will be given to the participant. The PI or designated staff member must document the process of obtaining Informed Consent through a detailed, accurate, and contemporaneous medical note, specifying the signed version, the date the document was signed, and how the process was carried out.

11.4.2 Special considerations

The procedures that will be performed during the conduct of the study do not pose any additional risk that should be considered apart from the procedures listed in the informed consent.

11.4.3 Modifications to informed consent

Any changes to the FCI constitute an amendment to this document and must be submitted for approval to the regulatory committees and authorities.

Such amendments may be implemented only after obtaining written approval from the Research Ethics Committee and the Regulatory Body (as applicable), except for an amendment that is required to eliminate an immediate danger to the study subjects.

re-consent process must be conducted for each subject affected by the amendment under the same conditions as those described above, in order to promptly communicate the new information contained in the document. The subject will be given a signed original of the amendment, and the researcher will retain the second original.

11.5 Confidentiality

All documents and information provided to the research center by the sponsor are strictly confidential. The PI expressly agrees that the data regarding his or her professional and clinical experience, provided to the sponsor in paper form and stored electronically, are solely for use in connection with his or her activities with the clinical study sponsor, in accordance with Good Clinical Practice.

The PI agrees that he and his team members will use the information only within the scope of this study, to carry out the protocol. This agreement is binding as long as the confidential information has not been publicly disclosed by the sponsor.

The clinical study protocol provided to the PI may be used by the PI and his or her team to obtain informed consent from the subjects for the study. The clinical study protocol, as well as any information derived from it, must not be disclosed to other parties without the sponsor's written authorization.

The PI will not disclose any information without the prior written consent of Laboratorios Sophia, SA de CV, except to representatives of the Competent Authorities, and only at their request. In the latter case, the researcher is obligated to inform Laboratorios Sophia, SA de CV before disclosing the information to these authorities.

The PI will complete and maintain a subject selection log, as well as the identification and enrollment list of each subject participating in the study. The researcher agrees to grant on-site access to the auditor and/or representatives of the Competent Authorities. The information will be treated in compliance with professional secrecy.

In the eCRF and all communications related to study subjects, they will be identified only by their study subject identification number, either the screening number or the allocation number. The information collected in this study will be exchanged between the sponsor and the research site and must be treated confidentially. The Health Authority, the IRB, the IC, the sponsor, the monitors/auditors, and third-party auditors will be the only bodies authorized to review the study documentation. If publications arise from this research project, under no circumstances will they contain information about the identification of the study subjects. If the study results are published, no personal information about the study subjects will be revealed.

The protection of personal data will be in accordance with the corresponding current regulations.

